Study Protocol
June 25, 2018
Revised March 3, 2020

Title

Clonidine versus Phenobarbital as Adjunctive Therapy

Primary Investigators

[name] and [name]

Research Support Staff

[name] [name]

Location

University of Tennessee Medical Center

Objective

To compare clonidine versus phenobarbital as adjunctive therapy in those infants who have failed monotherapy with morphine sulfate for neonatal abstinence syndrome (NAS).

Background/Significance/Intervention to be studied

Neonatal abstinence syndrome (NAS) is the result of sudden discontinuation of substances used or abused by the mother during pregnancy after delivery⁶. Opioids are the most common of these substances. The signs and symptoms associated with NAS include disturbances in the gastrointestinal, autonomic and central nervous systems⁷. Up to 80% of infants will fail behavioral intervention and require pharmacologic treatment to control the symptoms associated with NAS⁶. The American Academy of Pediatrics (AAP) supports the use of opioids as first-line pharmacotherapy for NAS⁶. Morphine sulfate is most commonly used in the United States for the treatment of NAS⁸. Despite appropriate treatment with opioids, many infants will often require adjunctive or second-line therapy. Phenobarbital and clonidine are both considered as adjunctive therapy for the treatment of NAS. Phenobarbital is considered the drug of choice for nonopiate withdrawal⁶ and is often used as adjunctive therapy in infants experiencing withdrawal due to maternal polysubstance abuse. However, there are concerns about the long-term neurodevelopment and exposure to alcohol in infants who receive phenobarbital. Studies have found clonidine to be an effective adjunctive therapy while a few recent studies have evaluated clonidine as initial therapy for the treatment of NAS². The limited data and concern for potential hypotension along with rebound hypertension may limit its use. Studies have compared morphine sulfate versus clonidine as initial therapy² and clonidine versus phenobarbital as in combination with morphine sulfate as initial therapy¹. However, there are no current studies comparing clonidine and phenobarbital as adjunctive therapy in infants who have failed monotherapy with morphine sulfate for the treatment of NAS.

Study Endpoints

The primary endpoint of this study is the **length of morphine sulfate therapy** ~~time from initiation of adjunctive therapy until hospital discharge in the two groups~~. Secondary end points include **time from initiation of adjunctive therapy until hospital discharge in the two groups**, length of stay, ~~length of morphine sulfate therapy~~, percentage of patients requiring triple therapy, safety and readmission rates.

Number of subjects

Approximately 50 patients will be enrolled in the study.

Inclusion / Exclusion Criteria

Inclusion Criteria

Infants greater than or equal to 35 weeks admitted to the neonatal intensive care unit (NICU) who have failed monotherapy with morphine sulfate will be eligible for enrollment in the study. Infants considered to have failed morphine sulfate therapy are those whose dose exceeds 0.15 mg (0.4 mL) q3h or have failed two attempts at weaning after initial stabilization.

Exclusion Criteria

Infants who develop NAS due to iatrogenic causes (analgesia or sedation), are unable to take oral medications at any point during their treatment or are in the custody of the department of child protective services with no legal guardian identified at the time of enrollment will be excluded.

Recruitment Methods

Subjects will be identified through medical record screening, contact with investigators patients in the clinical setting and referral from non-investigators (physicians, nurse practitioners or physician assistants).

Consent process

- An informed consent will be obtained from the parent or legal guardian for all infants enrolled in the study.
- A notice of research will be provided with the admission documents to the parent/legal guardian of all infants being admitted for NAS. If the patient fails monotherapy, the informed consent interview will be conducted and consent obtained over the phone. The full signed consent will be left at the patient bedside and given to the parent/legal guardian at their next visit to the hospital.

- The informed consent interview will be conducted over the phone by study personnel if the legal guardian is not present at the time it is determined that an adjunctive agent is needed to control the study participants' symptoms of NAS. Documentation of consent by the legal guardian will be noted by the study investigator and a witness. A copy of the informed consent will be left at the subject bedside to be provided to the legal guardian at the next visit to the NICU.

Methodology

Study Design

This study will be a prospective, single-site, randomized, open-label study with institutional review board (IRB) approval. The study will be conducted in the neonatal intensive care unit (NICU) at the University of Tennessee Medical Center.

Study Treatment

Infants who have failed monotherapy with morphine sulfate and have documented informed consent will be randomized to receive phenobarbital (20 mg/kg load, then 5 mg/kg/day divided q12h) or clonidine (6 mcg/kg/day divided q3h). The phenobarbital and clonidine suspensions are 4 mg/mL and 10 mcg/mL, respectively. Study agents will be titrated to achieve control of symptoms (previous 24-hour average FS less than or equal to 8). The phenobarbital dose will be adjusted to obtain a desired trough of 25 to 30 mcg/mL. Levels will be obtained on Day 6, then weekly thereafter. Infants with a trough less than 25 will receive an adjusted load of phenobarbital 1 mg/kg for every 1 mcg/mL increase from obtained level to achieve a desired level of 25 mcg/mL and a change in the maintenance dose using a ratio of desired to measured phenobarbital level. Clonidine will be escalated by 1.5 mcg/kg/day every 24 hours (maximum 12 mcg/kg/day) to achieve control of symptoms. Blood pressure (BP) is documented prior to each clonidine administration. If hypotension occurs while receiving clonidine, the current dose will be held. If more than 2 clonidine doses are held in the previous 24 hours the total daily dose will be decreased by 1.5 mcg/kg/day. After control of symptoms, morphine sulfate will be weaned by 0.02 mg (0.05 mL) every 24 hours as tolerated until off. Morphine sulfate will be weaned if symptoms are controlled, and no rescue doses are required in the previous 24 hours. A rescue dose of morphine sulfate 0.02 mg (0.05 mL) may be given every 3 hours for consecutive FS greater than or equal to 11 while morphine sulfate is being weaned and after discontinuation. Infants who experience return of symptoms and require more than 2 rescue doses in the preceding 24 hours after discontinuing morphine will be placed back on the 0.02 mg (0.05 mL) until symptoms are controlled. Once symptoms are again controlled, a second attempt to discontinue morphine sulfate will occur. After morphine sulfate has been discontinued for 24 hours and symptoms are still controlled, the study agent can be weaned. Clonidine will be weaned by 25% (based on the dose at time of morphine sulfate discontinuation) every 24 hours over 72 hours. Infants will be observed for return of symptoms and rebound hypertension for 48 hours prior to discharge. Blood pressure will be measured every shift for 48 hours after discontinuation of clonidine. Infants who experience rebound hypertension or fail to maintain control of symptoms after

discontinuation of clonidine will be placed back on the last effective dose until symptoms are controlled. Once symptoms are controlled, weaning will resume. Infants receiving phenobarbital will also be observed for 48 hours after the discontinuation of morphine sulfate prior to discharge. Phenobarbital will be weaned as an outpatient based on the standard taper used in the NICU for over 5 years (Table 1).

Table 1: Standard phenobarbital taper based on dose at discharge

Phenobarbital dose on day of discharge	Standardized phenobarbital taper initiated upon discharge
5.1 to 7 mg every 12 hours	6 mg two times a day for 1 week, then 4 mg two times a day for 1 week, then 2 mg two times a day for 1 week, then 2 mg once a day for 1 week, then stop
7.1 to 9 mg every 12 hours	8 mg two times a day for 1 week, then 6 mg two times a day for 1 week, then 4 mg two times a day for 1 week, then 2 mg two times a day for 1 week, then stop
9.1 to 11 mg every 12 hours	10 mg two times a day for 1 week, then 8 mg two times a day for 1 week, then 4 mg two times a day for 1 week, then 2 mg two times a day for 1 week, then stop
11.1 to 13 mg every 12 hours	12 mg two times a day for 1 week, then 8 mg two times a day for 1 week, then 6 mg two times a day for 1 week, then 2 mg two times a day for 1 week, then stop
13.1 to 15 mg every 12 hours	14 mg two times a day for 1 week, then 10 mg two times a day for 1 week, then 6 mg two times a day for 1 week, then 4 mg two times a day for 1 week, then stop

If symptoms are unable to be controlled with the study agent alone, the addition of the nonrandomized medication (phenobarbital/clonidine) may be initiated to control symptoms. Morphine, clonidine and phenobarbital, in that order, will be weaned per protocol.

The patient medical record will be reviewed to collect data about the subjects. This includes the patient’s electronic medical record and chart.

Risks to subjects

Risks to participants include side effects associated with study medication, potential increased length of stay/treatment compared to those patients receiving comparative medication and loss of confidentiality. Both of the study medications are commonly used in this patient population and considered standard of care with no evidence of superiority in the treatment of NAS.

Benefits to subjects

It is not known if one of the study medications will better control withdrawal symptoms, allow us to wean oral morphine faster, have fewer side effects or allow the infant to be

discharged from the hospital sooner. The knowledge gained from this research will help us determine if clonidine or phenobarbital could better control symptoms of withdrawal, have less side effects or allow children to be discharged from the hospital sooner.

Data Management

- The primary endpoint of time from initiation of adjunctive therapy until hospital discharge will be assessed using Mann-Whitney U test. Secondary Endpoints of length of stay and length of morphine therapy will also be assessed via Mann-Whitney U test. Side effects and readmission rate via chi-squared with an unadjusted odds ratio with 95% CI for 30-day readmission.
- A power analysis was completed for sample size (based on Surran et al findings with power to detect a 5-day difference in treatment time):

t tests – Means: Difference between two independent means (two groups)		
Analysis:	A priori: Compute required sample size	
Input:	Tail(s)	= Two
	Effect size d	= 3.0666667
	α err prob	= 0.05
	Power (1- β err prob)	= 0.80
	Allocation ratio N2/N1	= 1
Output:	Noncentrality parameter δ	= 4.3369216
	Critical t	= 2.4469119
	Df	= 6
	Sample size group 1	= 4
	Sample size group 2	= 4
	Total sample size	= 8
	Actual power	= 0.9475121

It is predicted that a sample size of 25 in each treatment group will be powered to detect 1.2-day difference in time from initiation of adjunctive therapy until hospital discharge.

- All paper research records containing data from individual subjects will be locked and stored. All electronic research records containing data from individual subjects will be computer password protected. All records will be accessible only to research personnel.

Withdrawal of Subjects

Subjects may withdraw their permission for participation in research at any time. Subjects will contact [name] in writing to let us know they are withdrawing their permission. □ The mailing address is [name]. □ At that time, we will stop further collection of any information. □ However, the health information collected before this withdrawal may continue to be used for the purposes of reporting and research quality.

References

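### Study Endpoints and Data Management name different primary endpoints, the 1.2-day detectable difference belongs to the former one, and length of morphine therapy has no counting rule

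*Combined protocol and SAP*

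**What the plan says.** Study Endpoints, as revised, states: "The primary endpoint of this study is the length of morphine sulfate therapy". The same revision moves time from adjunct start to hospital discharge to the secondary list.

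Data Management states: "The primary endpoint of time from initiation of adjunctive therapy until hospital discharge will be assessed using Mann-Whitney U test". It lists length of morphine therapy among the secondary endpoints, also to be compared by Mann-Whitney U test. It gives a sample-size table for a 5-day difference in treatment time (8 infants in total), then says that 25 per group "will be powered to detect 1.2-day difference in time from initiation of adjunctive therapy until hospital discharge". Readmission is to be summarised by "an unadjusted odds ratio with 95% CI for 30-day readmission".

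Study Treatment has rules for giving, stopping and restarting morphine:
- Entry: "Infants who have failed monotherapy with morphine sulfate and have documented informed consent will be randomized to receive phenobarbital".
- Rescue doses: these "may be given every 3 hours for consecutive FS greater than or equal to 11 while morphine sulfate is being weaned and after discontinuation".
- Restart: infants whose symptoms return and who "require more than 2 rescue doses in the preceding 24 hours after discontinuing morphine will be placed back on the 0.02 mg" dose until controlled, followed by a second attempt to stop.
- Next step: "After morphine sulfate has been discontinued for 24 hours and symptoms are still controlled, the study agent can be weaned".

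These are treatment rules. No section says from when the morphine length is counted, when it ends, or how rescue and restarted morphine enter it.

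**The concern.** Data Management is operative text, not a record of superseded wording. An analyst who follows it would report time to discharge as the primary result; one who follows Study Endpoints would report morphine length. The weaning rules load the two endpoints differently by arm, so this choice could decide what the trial concludes.

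The counting rule is a second, lesser gap. Every infant is on morphine before randomisation, and morphine can be given again after it is stopped, so two analysts could derive different lengths from one chart. The trial is open-label and its primary has already been changed once, so neither choice should be left until the analysis.

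**Working it through.** **1. The plan's own sample-size table.** Inputs from Data Management: two-sided 0.05, d = 3.0666667, equal groups. For a two-sample t-test the noncentrality is d × √(n/2) with 2n − 2 degrees of freedom. With n = 4: 3.0666667 × √2 = 4.3369, critical t 2.4469 on 6 df, power 0.9475, as printed. With n = 3 power is 0.799, so 4 per group is correct for that input.

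**2. The 1.2-day sentence.** At 25 per group (48 df), two-sided 0.05 and 80% power, the t-test detects d = 0.8087. The stated 1.2 days therefore implies an SD of 1.2 / 0.8087 = 1.48, about 1.5 days. No SD is printed for either endpoint.

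**3. Minimum stay after morphine stops** (Study Treatment, infants on one adjunct only).

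| Arm | Steps | Total |
|---|---|---|
| Clonidine | 24 h off morphine + 72 h wean + 48 h observation | 144 h |
| Phenobarbital | 48 h observation; taper continues at home | 48 h |

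Difference: 144 − 48 = 96 h, or 4 days. This takes the 48 h observation to follow the last clonidine dose, which fits the 48 h of blood pressure checks after clonidine stops. Even without those 48 h the difference is 96 − 48 = 48 h, or 2 days, still more than 1.2 days. The difference is part of time to discharge and is not part of morphine length.

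**4. Detectable difference for the current primary.** The planned test is the Mann-Whitney. Dividing 0.8087 by the square root of its efficiency relative to the t-test gives 0.8087 / √0.955 = 0.828 SD for normal data and 0.8087 / √0.864 = 0.870 SD at the lower bound for a pure shift. The SDs below are assumptions.

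| Assumed SD of morphine length | t-test (0.81 SD) | Mann-Whitney (0.83-0.87 SD) |
|---|---|---|
| 3 days | 2.4 days | 2.5-2.6 days |
| 5 days | 4.0 days | 4.1-4.4 days |
| 8 days | 6.5 days | 6.6-7.0 days |

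**5. Counting.** Invented chart: first morphine on day 1, randomised on day 6, scheduled morphine through day 16, restarted on days 20-21. Days are counted inclusively.

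| Origin | Elapsed to last dose | Days given | To first stop |
|---|---|---|---|
| First dose | 21 | 16 + 2 = 18 | 16 |
| Randomisation | 21 − 5 = 16 | 11 + 2 = 13 | 11 |

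Elapsed time counts the three morphine-free days (17-19) as therapy. Rescue doses add another choice: two or fewer in 24 h after discontinuation trigger no restart, so the last scheduled dose and the last dose of any kind can fall on different days.

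**The case against.** The strongest reply is that this is mostly a label left unrevised. Data Management does specify a test for morphine length, and it is the same Mann-Whitney test, so a reader who infers that the current primary has no planned analysis would be wrong. That stands, but the primary designation and the 1.2-day sentence still conflict with Study Endpoints.

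It would also be too strong to say that the whole sample-size calculation concerns the former primary. The 8-infant table is labelled treatment time, and the cited trial's title refers to morphine therapy days, so the table may relate to the current primary. Only the 1.2-day sentence is explicitly tied to time to discharge.

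Three further inferences are tempting, and the documents do not support them.
- *Days before randomisation bias the comparison.* They precede the adjunct, so they can add noise or chance imbalance, not bias. Counting the whole course is a legitimate reading, and counting from randomisation would change what is estimated.
- *The longer clonidine stay inflates false positives.* Any figure would need a restart rate, a timing pattern and an SD, none of which is given. The 144 h is inpatient time, not an established window for restarting morphine: after clonidine stops, the response named is a return to clonidine, and the text neither provides for nor excludes morphine. Restarts during the clonidine wean are also partly a real effect of that strategy.
- *The primary was changed in the light of results.* The revision is dated March 3, 2020; enrolment status at that date is not given.

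**Conclusion.** The conflict between the two sections is certain and should be resolved before analysis. Following Data Management as written would test, as primary, an endpoint that Study Endpoints has made secondary, with a detectable difference stated for that endpoint.

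The gap of about 4 days is a protocol minimum for infants on one adjunct. The realised gap may differ, since infants may stay longer for other reasons and morphine length itself may differ by arm. It is nevertheless larger than the 1.2 days the trial says it can detect.

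For morphine length no detectable difference can be stated without an assumed SD. The 1.2 days would carry over only if that SD were also about 1.5 days.

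The missing counting rule is also certain. How often it would matter is unknown, because no restart or rescue frequency is given; the 11 to 21 days come from one invented chart.

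**What to change.** 1. In Data Management, name length of morphine therapy as the primary endpoint (Mann-Whitney U) and time from adjunct start to discharge as secondary.
2. Replace the 1.2-day sentence with a detectable difference for morphine length, giving the assumed SD and its source.
3. State one counting rule, identical in both arms:
   - one time origin, first morphine dose or randomisation, at the sponsor's choice, with the other as a sensitivity analysis;
   - days on which scheduled morphine is given, including restarted days, rather than elapsed time to the last dose;
   - one rule for rescue-only days, with the alternative as a sensitivity analysis.
4. Report restarts and rescue-only days by arm beside 30-day readmission. The inpatient period after morphine stops differs by arm, and a phenobarbital infant already at home could show a relapse only as a readmission.
5. Date the clarification relative to enrolment and make it before outcomes by arm are seen. If they have been seen, report the competing definitions as sensitivity analyses and say so.

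The cost is a wording amendment and a few extra tables; the data are to come from the medical record. The downsides are a further clarification to a primary already changed once and, unless the SD is as small as about 1.5 days, a less favourable detectable difference on paper.

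### The revised primary endpoint, morphine duration, is still analysed as a secondary and has no defined clock; adjusting for entry dose and failure criterion would be a cheap precision gain of unknown size

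*Combined protocol and SAP*

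**What the plan says.** **Endpoint.** Study Endpoints: "The primary endpoint of this study is the length of morphine sulfate therapy". The former primary, time from adjunct start to discharge, is struck out there and moved to the secondaries. No start or end of the morphine count is given.

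**Analysis.** Data Management: "The primary endpoint of time from initiation of adjunctive therapy until hospital discharge will be assessed using Mann-Whitney U test". Its next sentence puts morphine duration among the secondaries, also with Mann-Whitney. The detectable difference at 25 per arm (1.2 days) is stated for time to discharge. No covariate, stratification factor or effect estimate in days is named for morphine duration.

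**Entry and randomisation.** Inclusion Criteria admit infants "whose dose exceeds 0.15 mg (0.4 mL) q3h or have failed two attempts at weaning after initial stabilization". Study Treatment: "Infants who have failed monotherapy with morphine sulfate and have documented informed consent will be randomized to receive phenobarbital".

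**Morphine after randomisation.** Once symptoms are controlled, "morphine sulfate will be weaned by 0.02 mg (0.05 mL) every 24 hours as tolerated until off". Rescue doses are allowed "while morphine sulfate is being weaned and after discontinuation", and infants who need more than two in 24 hours "after discontinuing morphine will be placed back on the 0.02 mg (0.05 mL) until symptoms are controlled".

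**Data source.** Study Treatment: "The patient medical record will be reviewed to collect data about the subjects".

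**The concern.** Two current sections name different primary endpoints. The one now designated primary cannot be computed without choices that the plan does not make. Does the count start at the first morphine dose or at randomisation? Does it end at the first discontinuation, or after later rescue doses and restarts? Two analysts could reach different values for the same infant. In an open-label trial, such choices should be fixed before outcomes are compared by arm.

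A second, lesser matter is unused information. The wean proceeds in fixed steps, so the dose at randomisation sets a minimum number of remaining morphine days. Dose and route of entry are both known before randomisation, and the planned test uses neither. With about 50 infants, free precision is worth considering.

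**Working it through.** **1. The plan's own figures.** With a two-sided α of 0.05, d = 3.0666667 and 4 per arm, the noncentrality is 3.0667 × √(4/2) = 4.337, critical t (6 df) is 2.447 and power is 0.9475. All three match Data Management. At 25 per arm the t test has 80% power at 0.809 SD. The stated 1.2 days therefore implies an SD of 1.2/0.809 = 1.48 days, whereas 5 days with d = 3.0667 implies 5/3.0667 = 1.63. Neither is given as an SD of morphine duration under the current definition, so SDs of 3, 5 and 7 days are assumed below.

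**2. Why entry dose should predict.** Infants entering on dose are above 0.15 mg (0.4 mL). 0.15/0.02 = 7.5 and 0.4/0.05 = 8, so they need at least 8 daily steps. Infants entering only by two failed weans are at or below that dose and need 8 or fewer. This is a minimum, not a forecast, because weaning is as tolerated. That the entry route itself is prognostic is an inference: failed-wean infants may have fewer steps but take longer over each.

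**3. Normal-theory power, 25 per arm.** Adjustment multiplies the variance by (1 − R²). Estimating two covariates costs a factor of 47/45 = 1.044 on average, so the break-even R² is 1 − 45/47 = 4.3%. The adjusted rows use 46 residual df and average over chance imbalance.

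| | Power at 0.6 SD | Power at 0.8 SD | Equivalent n per arm, 25/((1 − R²) × 1.044) |
|---|---|---|---|
| Unadjusted t test | 55% | 79% | 25 |
| R² = 0 | 53% | 77% | 23.9 |
| R² = 0.04 | 55% | 79% | 24.9 |
| R² = 0.10 | 57% | 81.5% | 26.6 |
| R² = 0.25 | 65% | 88% | 31.9 |

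**4. Skewed simulation against the planned test.** Days from randomisation = wean steps + gamma noise (shape 2), scaled to the assumed total SD, with an effect of 0.8 SD. Dose-route infants have 8 or 9 steps.
- Narrow scenario: 80% enter on dose and the rest have 5-8 steps. Step variance = (0.8 × 0.25 + 0.2 × 1.25) + 0.16 × 2² = 1.09.
- Wide scenario: 50% enter on dose and the rest have 2-7 steps. Step variance = (0.5 × 0.25 + 0.5 × 2.92) + 0.25 × 4² = 5.58.

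R² is step variance divided by SD². Runs: 20,000 per cell at SD 5, 8,000 at SD 3 and SD 7.

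| SD (days) | Narrow: R²; Mann-Whitney to rank ANCOVA | Wide: R²; Mann-Whitney to rank ANCOVA |
|---|---|---|
| 3 | 0.12; 85% to 89% | 0.62; 77% to 99% |
| 5 | 0.04; 87.4% to 87.9% | 0.22; 83.4% to 90.7% |
| 7 | 0.02; 87.0% to 87.2% | 0.11; 86% to 89.5% |

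With no prognostic value in either covariate (SD 5), power goes from 88.3% to 87.1%. If failed-wean infants take 2 days per step (SD 5, half entering on dose), it goes from 83.6% to 89.3% with both covariates but only to 84.1% with dose alone, which is the reason for including the criterion. Type I error of rank ANCOVA at SD 5 was 4.6-5.1%.

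**5. The clock.** Let s be the ratio of pre- to post-randomisation SD and ρ their correlation. Counting all morphine days multiplies the variance by 1 + s² + 2ρs. At ρ = 0 this is 1.09 for s = 0.3 and 2.00 for s = 1. At ρ = −0.3 and s = 0.3 it is 0.91. Starting at randomisation may therefore help precision or slightly harm it. The case for it is that it defines the endpoint and leaves out days that the study agent cannot affect.

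**The case against.** The strongest reply is that adjustment is a preference. The Mann-Whitney test is valid, dose fixes only a minimum duration, the prognostic value of the failure criterion is inferred, and at the low end of the assumed range the gain is nil. Any single range of gains is also the product of an assumed SD. All of this stands, and it is why adjustment is offered as an improvement and not as a correction of an error.

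Four stronger readings are tempting, and the documents do not support them.
- *The current primary has no stated analysis.* Data Management does assign it Mann-Whitney, the same test as for the former primary. The label is stale; what is open is which endpoint is primary and how it is measured.
- *The trial can detect only 0.81 SD.* That is a t-test figure. In the skewed scenarios the planned Mann-Whitney test exceeds 80% power at 0.8 SD in most cases; the exception is the wide scenario at SD 3 (77%).
- *The unadjusted analysis, or counting pre-randomisation days, biases the comparison.* Both quantities precede randomisation, so the issue is precision and definition.
- *The endpoint was changed after outcomes were seen.* The title page gives an original date of June 2018 and a revision of March 2020, and nothing on what was known at the revision.

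It is also fair to object that rank ANCOVA gives no estimate in days, and that an unadjusted Hodges-Lehmann interval may disagree with its p-value. The plan has to say so.

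**Conclusion.** The conflict between Study Endpoints and Data Management is plain on the text, as is the missing clock. Both need correcting whatever the covariates are worth. Prespecified adjustment is worth adding to the same amendment, with medium confidence. It gains from nothing to about 9 points at 0.8 SD by normal theory (R² 4-25%), and from about 0 to 21 points in the skewed scenarios as the assumed SD falls from 7 to 3 days. It loses 1-2 points if both covariates are uninformative. These sizes rest on assumed SDs, dose distributions and R², because the documents supply none for this endpoint. The validity of the planned test is not in question.

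**What to change.** 1. Amend Data Management so that morphine duration is the primary analysis, in all randomised infants as assigned. Count from randomisation to the last morphine dose of any kind, including restarts and rescue doses after discontinuation. Report total morphine days as supportive. This defines the measurement only and changes no dosing or weaning rule.
2. Restate the detectable difference at 25 per arm for this endpoint, giving the SD and its source. State how infants withdrawn before their last morphine dose are handled, since data collection stops at withdrawal.
3. As an improvement, prespecify rank ANCOVA as the primary test: pooled ranks of the outcome on arm, rank of morphine dose at randomisation, and failure criterion (two failed weans, yes/no). Keep the unadjusted Mann-Whitney test and a Hodges-Lehmann difference in days with 95% CI as supportive. State that this interval is unadjusted and may not agree exactly with the primary p-value.

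Fix all of this before outcomes are compared by arm.

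**Cost.** A protocol and SAP amendment, since the endpoint definition is sharpened, and two baseline fields that should already be in the record being reviewed. No extra infants are needed. The adjusted analysis spends two degrees of freedom and about 4% in variance, its two covariates overlap, and it is harder to explain than Mann-Whitney.

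### Blood pressure has a dense schedule on clonidine and none stated on phenobarbital, so an unadjusted comparison of hypotension is likely to over-detect it on clonidine unless charting is about as frequent in both arms

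*Combined protocol and SAP*

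**What the plan says.** **Clonidine arm.** Study Treatment gives clonidine every three hours and says "Blood pressure (BP) is documented prior to each clonidine administration". It adds an action rule, "If hypotension occurs while receiving clonidine, the current dose will be held", and a follow-up schedule: "Blood pressure will be measured every shift for 48 hours after discontinuation of clonidine".

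**Phenobarbital arm.** Dosing is every 12 hours. The parallel monitoring sentence is "Infants receiving phenobarbital will also be observed for 48 hours after the discontinuation of morphine sulfate prior to discharge". It does not mention blood pressure, and no other section supplies a schedule for this arm.

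**Endpoint and test.** Study Endpoints lists among the secondary endpoints "percentage of patients requiring triple therapy, safety and readmission rates". Data Management gives the analysis: "Side effects and readmission rate via chi-squared with an unadjusted odds ratio with 95% CI for 30-day readmission". There is no list of side effects, no definition of hypotension, no common schedule or window, and no adjustment for the number of readings.

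**Data source.** The design is open-label, and the data come from review of the medical record and chart.

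**The concern.** The chance that an infant has at least one low reading rises with the number of readings taken. If one arm is read 8 times a day and the other less often, the two proportions entering the chi-squared test are not measured in the same way. A difference can then appear with no difference in true risk.

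Hypotension and rebound hypertension are the clonidine harms that the Background names as possibly limiting its use. The Benefits section says the trial should help show which drug has fewer side effects. An excess of charted hypotension on clonidine could not be separated from the effect of looking more often.

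The observation windows differ too, in the same direction. After morphine stops, an uncomplicated clonidine course stays in hospital for 24 h, then a 72 h wean, then 48 h of observation: 24 + 72 + 48 = 144 h. The phenobarbital course has 48 h before discharge and is tapered as an outpatient.

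**Working it through.** The plan gives no blood-pressure or hypotension figure to reproduce. Its only computed design figure is the t-test output. That output does reproduce: d = 3.0666667 with 4 per group gives noncentrality 4.3369, critical t 2.4469 and power 0.9475. Nothing below depends on it.

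**Inputs from the documents**
- Clonidine readings: 24 h / 3 h = 8 a day (Study Treatment).
- Infants per arm: 25 (Data Management).
- Two-sided 0.05: stated for the power analysis, assumed here for the side-effect test.

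**Assumptions, because the documents are silent**
- 10 days on study drug.
- Per-reading chance of a low value p = 0.25%, 0.5% or 1%, the same in both arms.
- Readings independent; one low reading counts as an event.
- Uncorrected chi-squared.
- Phenobarbital readings a day, r: varied from 2 to 8.

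**Step 1. Share of infants with at least one low reading**

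Clonidine: 1 − (1 − p)^(8 × 10). Phenobarbital: 1 − (1 − p)^(r × 10).

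For p = 0.5% and r = 2: 1 − 0.995^80 = 33% against 1 − 0.995^20 = 10%. At p = 0.25% the shares are 18% and 5%; at p = 1% they are 55% and 18%.

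**Step 2. How often the test declares a difference when none exists**

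This enumerates every pair of counts from two binomials of size 25 with the Step 1 rates and sums the probability of pairs that the test rejects.

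| Phenobarbital readings a day | p = 0.25% | p = 0.5% | p = 1% |
|---|---|---|---|
| 2 | 32% | 56% | 82% |
| 3 | 22% | 37% | 60% |
| 4 | 15% | 23% | 39% |
| 6 | 7% | 9% | 13% |
| 8 | 5.5% | 5.5% | 6.4% |

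At 2 a day, varying the time on drug from 7 to 14 days moves the range to 21%–91%. At p = 0.1% and 10 days, 2 a day gives only 7.7%. A continuity-corrected test turns the first row into 12%, 38% and 72%.

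**Step 3. A second model with episodes that persist**

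Hypotension episodes arise as a Poisson process and last L hours. Readings come every I hours and catch an episode with probability min(1, L/I). With a true risk of 20% in both arms and L = 3 h, clonidine readings find 20.0%:

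| Phenobarbital reading interval | Share found on phenobarbital | Trials with more on clonidine | False rejections |
|---|---|---|---|
| 6 h | 10.6% | 77% | 16% |
| 8 h | 8.0% | 85% | 24% |
| 12 h | 5.4% | 92% | 36% |
| 24 h | 2.8% | 97% | 53% |

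Over the same intervals, false rejections are 8–18% at a true risk of 10% and 22–74% at 30%. The bias disappears if phenobarbital infants are also read every 3 h, or if episodes last at least as long as the phenobarbital interval (12 h episodes read every 12 h, for example).

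**Step 4. With matched readings**

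Observed rates are then equal by construction. For true risks of 10–50% and episodes of 3 h or longer, the test rejects in 4.9–6.5% of trials, and either arm is equally likely to show more (43% v 43% at 20% true risk).

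**The case against.** A reader might infer that the comparison will find more hypotension on clonidine, or that phenobarbital infants are hardly measured. The documents do not support either.

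- **Routine charting is not stated.** Every subject is a NICU inpatient, and the whole chart is the data source, so unscheduled readings count. Silence about a schedule is not evidence of sparse readings. At 6 or 8 phenobarbital readings a day little or no bias remains. This stands, and it makes the point conditional.
- **Independent readings exaggerate the gap.** Low pressure persists within an episode and clusters within infants, and the hold rule makes later readings depend on earlier ones. This stands; the episode model generally shows the same direction, with sizes down to none.
- **The affected comparison is inferred.** The plan says only safety and side effects; hypotension is neither named nor defined. If an event meant clinically recognised or treated hypotension, the per-reading model would not apply. This stands as a condition. Hypotension remains the obvious candidate, since it is the adverse effect with an action rule during treatment.
- **Triple therapy dilutes the contrast.** Phenobarbital infants given clonidine come under its blood-pressure rule. This stands, to an unknown extent.
- **Rebound hypertension is not covered by these figures.** It follows clonidine withdrawal and has no phenobarbital counterpart to compare.

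None of this supplies a common schedule. Nothing in the plan ensures that the arms are measured alike, and the planned test does not correct for it if they are not.

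**Conclusion.** The concern holds in conditional form. The text confirms the asymmetry in scheduled readings. If blood-pressure events are among the side effects compared, and phenobarbital infants are charted materially less often than every three hours, the unadjusted chi-squared comparison is biased towards more hypotension on clonidine.

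Under the stated assumptions the false-signal rate runs from about the nominal 5–6% at equal charting to 82% at 2 phenobarbital readings a day. No single value in that range can be called the trial's own, because routine frequency, episode length and event definition are all unstated. Even where the bias is present, a trial of 25 against 25 need not show the excess. This affects a secondary endpoint and not the efficacy comparison. It should be settled before the side-effect analysis is run.

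**What to change.** In Data Management, state that the between-arm comparison of hypotension:

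- uses one analysis definition of the event, applied alike in both arms;
- counts only readings from a schedule present in both arms, for example the first charted blood pressure of each nursing shift;
- covers the same window in both arms, from start of study agent to 48 h after morphine stops.

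Report pre-dose clonidine readings, held doses and post-clonidine rebound hypertension descriptively for infants given clonidine, with no between-arm test. The common window cannot carry rebound hypertension: clonidine weaning starts no earlier than 24 h after morphine stops and runs 72 h, so a window closing at 48 h ends during the wean. Because the window's length follows the duration of morphine, also show the number of counted readings per infant by arm.

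The cost is a few sentences of analysis text and no new data collection. Bedside monitoring and dosing do not change. The fix assumes that blood pressure is charted at least once per shift in both arms, which the sponsor should confirm. The downside is that hypotension seen only on the extra clonidine readings becomes descriptive, so the formal comparison rests on fewer events.
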